## **2. LIST OF ABBREVIATIONS**

Term	Definition / description
AE	Adverse event
BRPM	Blinded report planning meeting
CR	Complete response
CTCAE	Common Terminology Criteria for Adverse Events
CTP	Clinical Trial Protocol
eCRF	Electronic case report form
ECG	Electrocardiography
ECOG	Eastern Cooperative Oncology Group
EGFR	Epidermal growth factor receptor
EMA	European Medicines Agency
EoT	End of treatment
HEP C	Hepatitis C
HIV	Human Immunodeficiency Virus
ICH	International Conference on Harmonisation
IPV	Important protocol violation
Max	Maximum
MedDRA	Medical Dictionary for Regulatory Activities
mg	Milligram
Min	Minimum
N	Denotes number of patients
NSCLC	Non-small cell lung cancer
PD	Progressive disease
PP	Per-protocol
PT	Preferred term
SAE	Serious adverse event
SD	Standard deviation
SOC	System organ class

---

Term	Definition / description
TKI	Tyrosine kinase inhibitor
TS	Treated set
TSAP	Trial statistical analysis plan
TTSP	Time to symptomatic progression

### **3. INTRODUCTION**

As per ICH E9, the purpose of this document is to provide a more technical and detailed elaboration of the principal features of the analysis described in the protocol, and to include detailed procedures for executing the statistical analysis of the primary and secondary variables and other data.

This TSAP assumes familiarity with the Clinical Trial Protocol (CTP), including Protocol Amendments. In particular, the TSAP is based on the planned analysis specification as written in CTP Section 7 “Statistical Methods and Determination of Sample Size”. Therefore, TSAP readers may consult the CTP for more background information on the study, e.g., on study objectives, study design and population, treatments, definition of measurements and variables, planning of sample size, randomization.

SAS® Version 9.4 will be used for all analyses.

#### **4. CHANGES IN THE PLANNED ANALYSIS OF THE STUDY**

The definition of time to symptomatic progression (TTSP) has been clarified in [Section 7.5.2](#).

## **5. ENDPOINT(S)**

This is an open-label, multi-centre, non-randomised, uncontrolled, single arm trial designed to evaluate the safety, tolerability and efficacy of afatinib (Giotrif®) in patients with locally advanced or metastatic non-small cell lung cancer (NSCLC) harboring EGFR mutation(s) and have never been treated with an EGFR-TKI. After the initial screening visit, patients will enter the open-label treatment period with safety visits at approximately every 28 days until the end of the trial. The trial objective is to evaluate the safety and tolerability of afatinib (Giotrif®) in this cohort of patients. Of main interest are adverse events, collected throughout the study.

No specific tumour measurements are required in this program. Data regarding tumour assessments are performed at clinic visits as per local standard of care for NSCLC.

### **5.1 PRIMARY ENDPOINT**

- Number of patients with serious adverse events (SAEs).

### **5.2 SECONDARY ENDPOINTS**

#### **5.2.1 Key secondary endpoint**

There are no key secondary endpoints.

#### **5.2.2 Secondary endpoints**

- Number of patients with drug related adverse events.
- Time to symptomatic progression (TTSP)

## **6. GENERAL ANALYSIS DEFINITIONS**

### **6.1 TREATMENT**

There is only one treatment in this study, which is afatinib. The starting dose for all patients is 40 mg with an option to reduce the dose to 30 mg or 20 mg based on individual tolerability. Unless otherwise stated, for all analyses, treated patients will be presented under the starting dose.

The following study periods based on key visit dates and actual start and stop dates of study treatment administration are defined:

- Screening: From day of informed consent to day prior to starting study treatment.

Special handling rule:

If informed consent date = date of first administration of active treatment in the trial, derive start of screening phase on the day of informed consent – 1 day.

- On-treatment: From day of first administration of study treatment to the day of last administration of study treatment.
- Residual effect period (REP): From day after last administration of study treatment to the 28th day after last administration of study treatment.
- Follow-up: After the residual effect period and up to the last per protocol contact.
- Post-study: After the last per protocol contact but entered in the database before database lock.

For safety summaries data recorded up to 28 days after last administration of study treatment will be considered as on-treatment (i.e. the actual on-treatment and REP periods defined above will be combined into one 'on-treatment' analysis period).

Safety data recorded after follow-up period will be listed as post-study events but not tabulated.

### **6.2 IMPORTANT PROTOCOL VIOLATIONS**

No per protocol analysis will be performed for this study; however patients with potentially important protocol violations (IPVs) will be documented. The following list of potentially IPVs will be used; note that this is a working list and may not be finalised until the final Blinded Report Planning Meeting (BRPM) prior to database lock.

Table 6.2: 1 Important protocol violations

Category / Code	Description	Comment/Example	Efficacy / Safety
A	Entrance Criteria Not Met		
A1	Inclusion Criteria Not Met		
A1.1	Not locally advanced or metastatic Non-Small Cell Lung Cancer (NSCLC)	Inclusion criteria IN1 not met	E
A1.2	No presence of Epidermal Growth Factor Receptor (EGFR) mutation in tumour biopsy.	Inclusion criteria IN2 not met or EGFR mutation negative	E
A1.3	Male or female patients age <18 years	Inclusion criteria IN3 not met or patient's age <18 years	E/S
A1.4.1	Inadequate organ function as defined in protocol version 2.	Inclusion criteria IN4 not met	E/S
A1.4.2	Inadequate organ function as defined in protocol version 3.	Inclusion criteria IN4 not met	E/S
A1.5	ECOG score not between 0 – 2	Inclusion criteria IN5 not met, or baseline ECOG score not between 0-2.	E/S
A2	Exclusion Criteria Met		
A2.1	Prior treatment with an EGFR tyrosine kinase inhibitor (TKI)	Exclusion criteria EX1 met	E
A2.2.1	hormonal anti-cancer treatment within 2 weeks prior to start of trial treatment as defined in protocol version 2.	Exclusion criteria EX2 met	E
A2.2.2	Use of anti-cancer treatment within 2 weeks prior to start of trial treatment as defined in protocol version 3.	Exclusion criteria EX2 met	E
A2.3.1	Radiotherapy within 14 days prior to drug administration as defined in protocol version 2.	Exclusion criteria EX3 met	E
A2.3.2	Radiotherapy within 4 weeks prior to drug administration as defined in protocol version 3.	Exclusion criteria EX3 met	E
A2.4	Major surgery within 4 weeks from day 1 of first dose of afatinib, or minor surgical procedures including placement of an access device or fine needle aspiration within 7 days, or diagnostic or palliative video-assisted thoracoscopic surgery (VATS) within 14 days.	Exclusion criteria EX4 met	E/S
A2.5	Known hypersensitivity to afatinib or any of its excipients	Exclusion criteria EX5 met	S
A2.6	History or presence of clinically relevant cardiovascular abnormalities or myocardial infarction within 6 months prior to starting trial treatment	Exclusion criteria EX6 met	S

Category / Code	Description	Comment/Example	Efficacy / Safety
A2.7.1	Women of Child-Bearing Potential or man who is able to father a child, unwilling to be abstinent or use adequate contraception prior to trial entry, for the duration of trial participation and for at least 2 weeks after treatment has ended as defined in protocol version 2.	Exclusion criteria EX7 met	S
A2.7.2	Women of Child-Bearing Potential or man who is able to father a child, unwilling to be abstinent or use adequate contraception prior to trial entry, for the duration of trial participation and for at least 4 weeks after treatment has ended as defined in protocol version 3.	Exclusion criteria EX7 met	S
A2.8	Childbearing potential who: a. are nursing or b. are pregnant or c. are not using an acceptable method of birth control, or do not plan to continue using this method throughout the trial and/or do not agree to submit to pregnancy testing required by this protocol	Exclusion criteria EX8 met	S
A2.9	Any history of or co-existing condition that, in the opinion of the investigator, would compromise the patient's ability to comply with the trial or interfere with the evaluation of safety for the trial drug	Exclusion criteria EX9 met	E/S
A2.10	Previous or concomitant malignancies at other sites, except effectively treated nonmelanoma skin cancers, carcinoma in situ of the cervix, ductal carcinoma in situ or effectively treated malignancy that has been in remission for more than 3 years and is considered to be cured.	Exclusion criteria EX10 met	E/S
A2.11	Requiring treatment with any of the prohibited concomitant medications that cannot be stopped for the duration of trial participation	Exclusion criteria EX11 met	E
A2.12	Known pre-existing interstitial lung disease	Exclusion criteria EX12 met	S
A2.13	Presence of poorly controlled gastrointestinal disorders that could affect the absorption of the trial drug based on investigator assessment	Exclusion criteria EX13 met	E
A2.14	Known active hepatitis B infection, active Hepatitis C (HEP C) and/or known Human Immunodeficiency Virus (HIV) carrier.	Exclusion criteria EX14 met	S
A2.15	Meningeal carcinomatosis	Exclusion criteria EX15 met	E/S
A2.16	Symptomatic brain metastases	Exclusion criteria EX16 met	E/S
B	Informed Consent		
B1	Informed consent not given	Inclusion criteria IN6 not met or consent date is missing	S
B2	Informed consent given too late	Inclusion criteria IN6 not met	S
B3	Re-consent for updated informed consent form not given or given too late	IPV if the change affects the safety and right of the patient	S

Category / Code	Description	Comment/Example	Efficacy / Safety
C	On Study		
C1	Incorrect trial medication dose affecting the safety of the patient		S
C2	Local lab test not done affecting the safety of the patient		S
C3	Expired IP taken by patient and confirmed by CTSU as not suitable for administration		E/S
C4	Other PV affecting efficacy		E
C5	Other PV affecting safety		S

**Note:** Missing visits, evaluations, and tests will be considered missing data, not protocol deviations. All the potential IPV's listed in the table will be identified programmatically.

### **6.3 PATIENT SETS ANALYSED**

#### Enrolled set (ES)

The enrolled set consists of all patients who signed informed consent.

#### Treated set (TS)

All planned analyses will be based on the Treated Set (TS) which includes all patients who were dispensed trial medication and are documented to have taken at least one dose of investigational treatment (afatinib).

## **6.5 POOLING OF CENTRES**

This section is not applicable because there will be no pooling of centres or countries and no modelling thereof.

## **6.6 HANDLING OF MISSING DATA AND OUTLIERS**

Missing or incomplete AE dates are imputed according to BI standards (see “Handling of missing and incomplete AE dates”).[\(1\)](#)

For efficacy data, the following rules will apply:

In addition, time since first diagnosis of NSCLC will be calculated from the date of diagnosis and the date of the start of the study treatment. As the date of diagnosis is likely to be partial in many cases, the following rules will be used

- If day is missing but month and year are present, impute to first day of the month.
- If only year is present, set to January 1st.

For partial treatment discontinuation date, the following logic is applied:

If month and year are known but day is missing, then use date of death if within the same month for a patient who died. Otherwise use last day of the month.

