6.1.4 End of Treatment (EOT) visit

All patients should be evaluated at the end of their trial treatment. This visit should be completed on the day of the patient's last dose on trial medication or up to 14 days later.

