## **6.7 BASELINE, TIME WINDOWS AND CALCULATED VISITS**

Where a baseline value is required, this will be defined as the last non-missing value prior to first administration of afatinib.

The time windows for subsequent clinic visits is 28 -7/+2 days. The end of treatment (EoT) visit can be anything up to a maximum of 14 days after the last trial drug intake and the follow-up visit should be between 28 and 35 days after the EoT visit.

Nominal visit numbers as recorded in the eCRF will be used where required and there will be no windowing.

Study day will be calculated relative to the date of the first administration of study drug. The day prior to first administration of study drug will be 'Day -1' and the day of first administration of study drug will be 'Day 1'; therefore 'Day 0' will not exist.

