##### **Time to symptomatic progression (TTSP)**

Defined as the time (number of days) from first administration of afatinib to the date of first documented clinically significant symptomatic progression that required stopping afatinib according to investigator's assessment.

Patients will be considered to have clinically significant symptomatic progression if the reason for termination of trial medication is recorded as 'progressive disease' or 'worsening or AE of underlying cancer disease', on the termination of trial medication eCRF page.

Therefore TTSP will be derived as:

$TTSP \text{ [days]} = \text{date of last administration of trial drug (where 'progressive disease' or 'worsening or AE of underlying cancer disease' selected on the termination of trial drug eCRF page)} - (\text{date of start of treatment}) + 1$

Kaplan-Meier estimates and 95% confidence intervals for the 25th, median, and 75th percentiles of the survival distribution will be calculated for TTSP. Greenwood's standard error estimate will be used. Kaplan-Meier curves will also be produced.

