##### *Censoring rules for TTSP:*

- For patients who have 'other AE', 'non-compliance with protocol', 'lost to follow-up', 'patient refusal to continue taking trial medication' or 'other' recorded on the termination of trial medication eCRF page, these patients will be censored at the date of last administration of the trial drug recorded on the termination of trial drug page;
- For patients who are still on treatment, these patients will be censored at cut-off date for interim analysis and at the date of EOT visit for final analysis.

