### **7.8.1 Adverse events**

The intensity of adverse events were classified and recorded according to the Common Terminology Criteria for Adverse Events (CTCAE) version 3.0 in the eCRF.

Unless otherwise specified, the analyses of adverse events will be descriptive in nature. All analyses of AEs will be based on the number of patients with AEs and NOT on the number of AEs.

Furthermore, for analysis of AE attributes such as duration, severity, etc. multiple AE occurrence data on the CRF, will be collapsed into AE episodes provided that all of the following apply:

- The same MedDRA lowest level term was reported for the occurrences
- The occurrences were time-overlapping or time-adjacent (time-adjacency of 2 occurrences is given if the second occurrence started on the same day or on the day after the end of the first occurrence)
- Treatment did not change between the onset of the occurrences OR treatment changed between the onset of the occurrences, but no deterioration was observed for the later occurrence

For further details on summarization of AE data, please refer to the guideline 'Handling and summarization of adverse event data for clinical trial reports and integrated summaries' ([2](#)) [001-MCG-156]

The analysis of adverse events will be based on the concept of treatment emergent adverse events. That means that all adverse events occurring between first study drug intake until 28 days after last study drug intake will be assigned to be treatment-emergent. All AEs occurring outside of this period will be handled according to the treatment definition period definitions detailed in [Section 6.1](#) and will only be listed unless stated otherwise.

An overall summary of adverse events will be presented. This summary will exclude the rows ‘Severe AEs’, ‘Significant AEs’ and ‘Other significant AEs’ but will include additional

rows for 'AEs leading to dose reduction' and 'AEs by highest Common Terminology Criteria (CTC)' grade.

The frequency of patients with adverse events will be summarised by highest CTC grade (grades 3, 4, 5 and all grades including also grade 1 and 2), treatment, primary system organ class (SOC) and preferred term (PT) for each of the following AE tables:

- All AEs collected
- Drug related AEs.
- AEs leading to dose reduction.
- AEs leading to treatment discontinuation.
- Drug related AEs leading to treatment discontinuation
- Serious AEs.
- Drug related serious AEs.
- AEs leading to death.

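### SAP 6.6 sets a discontinuation date with a missing day to month-end, bounded only by a same-month death, so the imputed last dose can fall after the EOT visit or the data cut-off

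*SAP*

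**What the plan says.** SAP 6.6 covers a treatment discontinuation date whose month and year are known but whose day is missing. If the patient died, "then use date of death if within the same month for a patient who died". For all other cases: "Otherwise use last day of the month". No visible text mentions the EOT visit or the data cut-off as a limit.

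The timing of the EOT visit is fixed elsewhere. Protocol 6.1.4: "This visit should be completed on the day of the patient's last dose on trial medication or up to 14 days later". SAP 6.7 agrees: "The end of treatment (EoT) visit can be anything up to a maximum of 14 days after the last trial drug intake".

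The last-dose date is used in several places:
- **TTSP event** (SAP 7.5.2): "date of last administration of trial drug (where 'progressive disease' or 'worsening or AE of underlying cancer disease' selected" is the event date.
- **TTSP censoring** (SAP 7.5.2), for patients who stop for other reasons: "these patients will be censored at the date of last administration of the trial drug recorded on the termination of trial drug page". For patients still on treatment, "these patients will be censored at cut-off date for interim analysis and at the date of EOT visit for final analysis".
- **Exposure** (SAP 7.7): stop date minus start date plus 1.
- **Adverse events** (SAP 7.8.1): "all adverse events occurring between first study drug intake until 28 days after last study drug intake will be assigned to be treatment-emergent". Events outside that period are in general only listed.

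Protocol 7.4 has a separate rule for TTSP. If progression is known but its date cannot be obtained, the date of the last assessment is used.

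**The concern.** The default branch always picks the latest day the month allows. The schedule supplies a tighter bound, because a patient seen at EOT has already taken the last dose. The rule ignores that bound, so the analysis data can contain a last dose after the visit that closed treatment. For an analysis with a cut-off before month-end, a stop in the cut-off month with a missing day is likewise placed after the cut-off.

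The error has one direction. If the imputed date feeds the last-administration date, TTSP and exposure can only become longer. The treatment-emergent window can only extend later, which could bring in events that belong outside it. That window also governs the primary endpoint, the number of patients with serious adverse events (SAEs).

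**Working it through.** The plan gives no figure on this point, so there is nothing to reproduce. The check enumerates every possible last-dose day in a 365-day year.

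**Inputs.** Month-end rule (SAP 6.6); EOT gap g of 0 to 14 days (protocol 6.1.4, SAP 6.7); 28-day AE window (SAP 7.8.1). Assumptions: last-dose day uniform over the year, no death in the same month, and an EOT visit took place.

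**Overshoot.** For a month of length L and true day d, overshoot = L − d. Summed over a month this is L(L − 1)/2, which is 465 for 31 days, 435 for 30 and 378 for 28.
- Mean = (7 × 465 + 4 × 435 + 378)/365 = 5373/365 = 14.7 days.
- Range 0 to 30. It is above zero on 353 of 365 days (96.7%) and never negative.

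**Share of imputed dates after EOT.** The imputed date passes EOT when L − d > g.

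| EOT gap g | Days of 365 | Share past EOT | Maximum days past EOT |
|---|---|---|---|
| 0 | 353 | 96.7% | 30 |
| 7 | 7×23 + 4×22 + 20 = 269 | 73.7% | 23 |
| 14 | 7×16 + 4×15 + 13 = 185 | 50.7% | 16 |

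**Example.** True last dose 3 May, EOT 10 May, imputed 31 May. The imputed date is 21 days after EOT and 28 days after the true last dose. The AE window ends on 28 June instead of 31 May.

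**AE window.** At worst it ends 28 + 30 = 58 days after the true last dose. The follow-up contact, 28 to 35 days after EOT (protocol 6.1.5, SAP 6.7), falls 28 to 49 days after the last dose and asks about events that began since EOT. Some events from day 29 onward can therefore be on record and be moved into the tabulated period.

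**Trial level.** The share f of patients with a partial date is not in the documents. Mean exposure shift = f × 14.7:
- f = 1%: 0.15 days
- f = 5%: 0.7 days
- f = 10%: 1.5 days

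A simulation of 500 uncensored exponential times, with assumed medians of 330 and 420 days, moved the median TTSP by about 0.1 to 0.2, 0.6 to 0.7 and 1.5 to 1.6 days at the same three shares.

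**With the bound added.** Overshoot becomes min(L − d, g), at most 14 days. Averaged over gaps of 0 to 14 days, its mean falls from 14.7 to 5.8 days. The latest window end falls from day 58 to 28 + 14 = day 42.

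**The case against.** The strongest reply is that this is an edge case in a descriptive single-arm trial with no hypothesis tests. Much of that reply stands:

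- The last-dose date is recorded on the eCRF at EOT, at most 14 days after the event, so a missing day should be uncommon. SAP 6.6 expects many partial diagnosis dates but says nothing similar about discontinuation dates.
- Missing days may cluster in patients lost to follow-up without an EOT visit. For them an EOT bound changes nothing.
- Patients still on treatment are censored at the cut-off or the EOT visit and are unaffected. The cut-off problem concerns an optional interim analysis (protocol 7.3.4) and stops in the cut-off month.
- The 58-day window needs a true last dose on the 1st of a 31-day month, which is 7 days in 365. Routine AE collection stops 28 days after the last dose, and after the follow-up visit only related SAEs are reported. Counting too many SAEs is also the cautious direction.
- The efficacy rules in SAP 6.6 appear to be blanked out, so a further TTSP rule there cannot be excluded. Protocol 7.4 already points to a different date.

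A reader might infer that the rule has no upper limit at all, or that it gives an impossible date every time. The documents support neither. A same-month death does limit it, and with EOT 14 days after the last dose about half of the imputed dates do not pass EOT.

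None of this removes the defect. The discontinuation-date rule is visible in full, and for a patient with an EOT visit it can give a date that the plan's own schedule rules out.

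**Conclusion.** Wrong as written, with a small effect. The rule lacks a bound that the schedule provides, and its error cannot shorten TTSP, exposure or the AE window. A single patient can be off by up to 30 days, on average 14.7, under the stated assumptions. At trial level the shift is probably about a day or less unless partial dates are common, and their number is unknown.

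The conclusion about TTSP and the AE window rests on reading the treatment discontinuation date as the date of last administration, which the SAP does not state. It would be tempting to conclude that the primary SAE count is biased. The documents do not show that: the count changes only if a patient's sole qualifying SAE was recorded more than 28 days after the true last dose, and no estimate of such events is possible from the plan.

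**What to change.** Replace the rule in SAP 6.6 with one sentence: if only the day is missing, impute the earliest available of the last day of that month, the date of death, the EOT visit date and the data cut-off date.

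Death must sit inside the minimum, not in a branch of its own. With EOT on 5 May, death on 25 May and a last dose in May, a separate death branch would still impute 25 May, 20 days after EOT. If the minimum falls before the recorded month, the dates conflict and need a data query, not imputation.

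In addition:
- State whether the treatment discontinuation date is the date of last administration used in SAP 7.5.2 and 7.8.1.
- State which rule governs TTSP when the date is incomplete, this one or the last-assessment rule in protocol 7.4.
- Report how many dates were imputed.

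The cost is a few lines of SAP text and a small programming change. SAP 7.5.2 already uses the EOT and cut-off dates, and the date of death is on the eCRF, so nothing new has to be collected. The bound does not remove the error: up to 14 days can remain, still in the same direction.
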